### Psychosocial aspects

The management of psychosocial symptoms (anxiety and depression) has gained attention in cancer care. In this scenario, there is evidence showing the association between psychosocial and physical symptoms.

Gastrointestinal symptoms, particularly diarrhea, is one of the common side effects among cancer patients who are receiving sunitinib therapy, and it is known that mood could be influenced by gastrointenstinal manifestations and biological mechanisms (as abnormalities in the gut-brain axis, shared genetic factors, inflammation) in gastrointestinal chronic inflammatory diseases; however little is known about the relationship between psychosocial symptoms, bacteriomic profile and gastrointestinal toxicity in mRCC patients. Therefore, future studies should be conducted in order to understand this association.

To date, there is relatively limited data to characterize the symptoms of anxiety and depression in patients with renal cell carcinoma. There is no specific measure for assessing these symptoms in patients with mRCC, except for a recent guideline for screening, and assessment of anxiety and depressive symptoms in adults with cancer. Generalized Anxiety Disorder (GAD)-7 is recommended as a good measure to assess significant symptoms of anxiety, and the Patient Health Questionnaire for Depression (PHQ)-9 of depression. Both measures are based on the Diagnostic and Statistical Manual of Mental Disorders (DSM).

IRB Protocol No. 16088 Version Date: 06/12/2020

The GAD-7 is a one-dimensional self-administered scale designed to assess the presence of the symptoms of anxiety. Score is calculated by simple addition of the answers to each item. Scores for all 7 items range from 0 (not at all) and 3 (nearly every day). Therefore, the total scores ranges from 0 and 21, and may be categorized into four severity groups: minimal (0-4), mild (5-9), moderate (10-14) and serious (14-20).Questionnaire administration time is 5 minutes.

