The PHQ-9 focuses on the nine signs and symptoms of depression from the DSM, and has a dual-purpose, to establish a provisional disorder diagnosis and to provide a symptom severity score. High scores indicate increasing severity of depression. For a diagnosis of depression, five or more items must be scored as present more than half of the days or nearly every day. A PHQ-9 score of 5-9 indicates minimal depressive symptoms, a score of 10-14 is minor depression or major depression that is mild, a score of 15-19 is major depression, moderately severe, and a score > 20 indicates major depression, sever. Questionnaire administration time is 5 minutes.

Patients will be assessed for anxiety and depression at 2 distinct time-points: at baseline (before starting sunitinib - T1) and at week 13 (T2) to match the proposed assessments of stools and gastrointestinal toxicity.

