# Secondary Objectives:

 To determine if the Activia™ reduces the incidence of diarrhea for mRCC patients treated with VEGF-TKIs.

We will compare the rate of all grade diarrhea in patients who receive the dietary supplement and those who do note. The rate of grade 3/4 diarrhea will also be compared between the two groups. A Fisher's exact test with a 0.050 one-sided significance level will have 80% power to detect the difference between the Activia™ group proportion with diarrhea, ②₁, of 0.200 and a non-Activia™ proportion, ②₂, of 0.800 when the sample size in each group is 10.

2) To compare pre-treatment levels of circulating Treg cells and levels of peripheral STAT3 in patients with and without diarrhea with sunitinib therapy, and correlate with Bifidobacterium, other bacteria, and Activia™:

Treg quantity is a secondary measurement and an analysis will be carried out to evaluate whether Tregs expression differs in patients who develop diarrhea with VEGF-TKI therapy as compared to patients who do not. The distribution of the Treg quantity will be examined and log transformation may be applied if the distribution is skewed. Parametric or nonparametric test will be used to compare Tregs between the the diarrhea and non-diarrhea groups, and between the Activia™ and non-Activia™ groups.

3) To determine if patients with the diarrhea in mRCC patients treated with VEGF-TKI therapy have a lower baseline level of *Bifidobacterium spp*.

IRB Protocol No. 16088 Version Date: 06/12/2020

Once diarrhea has occurred, the Bifidobacterium spp may be reduced. We will compare the abundance of Bifidobacterium spp. Between diarrhea and non-diarrhea patients and the change in Bifidobacteria in patients who subsequently get diarrhea.

4) To explore association between psychosocial symptoms (anxiety and depression) and bacteriomic profile and gastrointestinal toxicity in mRCC patients treated with VEGF-TKIs. We will dichotomize the population based on low or high depression (and subsequently low and high anxiety). Using descriptive statistics, we will then assess differences in response rates, gastrointesntinal toxicity, microbial diversity and immune biomarkers.

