#### 8.2 Sample Size and Projected Accrual Rate and Study Duration

Twenty participants will be metastatic renal cell carcinoma will enroll to the study. Enrollment is expected to be completed in 3 years, and the study is expected to be completed in 3.5 years.

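### Depression and anxiety totals are split into low and high groups at no named cut or time point, and no analysis of the scores themselves is planned

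*Combined protocol and SAP*

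**What the plan says.** The objective in Section 8.1, item 4 is exploratory: "To explore association between psychosocial symptoms (anxiety and depression) and bacteriomic profile and gastrointestinal toxicity in mRCC patients treated with VEGF-TKIs". The method has two steps. First, "We will dichotomize the population based on low or high depression (and subsequently low and high anxiety". Then, "Using descriptive statistics, we will then assess differences in response rates, gastrointesntinal toxicity, microbial diversity and immune biomarkers". Section 8.2 sets the size: "Twenty participants will be metastatic renal cell carcinoma will enroll to the study".

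Both instruments give a numerical total. For the GAD-7, Section 2.1 (Psychosocial aspects) states: "Therefore, the total scores ranges from 0 and 21". The PHQ-9 has nine items scored 0 to 3 (Appendix E), and Section 2.1 says that it "has a dual-purpose, to establish a provisional disorder diagnosis and to provide a symptom severity score". Both are completed before treatment and at week 13 (Section 2.1; Section 4.1, Study Activity Table).

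Section 2.1 lists severity bands for each scale and an item-count rule for a depression diagnosis. Item 4 refers to none of these and does not say which of the two assessments defines the groups.

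**The concern.** Splitting a score treats all patients on one side of the cut as equal. In a sample of 20, that discards information the trial has already collected, and the aim of the objective is to look for association.

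The open cut is a second problem. Several band edges, the diagnostic rule and a median split are all available, each at two time points, and they can give different groups. If the choice is made after the data are seen, the reported pattern can depend on it.

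Small groups add to this. Section 2.2 puts diarrhea at roughly 50% of patients. A 4/16 split would then give expected cells of 4 × 0.5 = 2 and 2 in the high group, and 16 × 0.5 = 8 and 8 in the low group.

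Item 2 of the same section keeps Treg as a quantity, with a log transformation if it is skewed. Nothing explains why the psychosocial scores are handled differently.

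**Working it through.** The plan gives no power, precision or efficiency figure for item 4, so there is none to reproduce.

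**Inputs.** From the documents: n = 20. Assumed: a roughly normal score, a linear association with a continuous outcome, and a share p of patients in the high group.

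**Formula.** Relative efficiency of the split against the score is e = φ(c)² / [p(1 − p)], where c is the normal cut leaving p above it. The equivalent number of patients is 20e.

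| High/low | p | c | φ(c) | e | 20e | Loss |
|---|---|---|---|---|---|---|
| 10/10 | 0.50 | 0 | 0.399 | 0.637 | 12.7 | 36% |
| 6/14 | 0.30 | 0.524 | 0.348 | 0.576 | 11.5 | 42% |
| 5/15 | 0.25 | 0.674 | 0.318 | 0.539 | 10.8 | 46% |
| 4/16 | 0.20 | 0.842 | 0.280 | 0.490 | 9.8 | 51% |
| 2/18 | 0.10 | 1.282 | 0.175 | 0.342 | 6.8 | 66% |

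For example, at 4/16: 0.280² / (0.20 × 0.80) = 0.0784 / 0.16 = 0.490. A simulation at n = 20 agrees: the squared correlation between score and split averages 0.639 at 10/10 and 0.484 at 4/16.

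**Meaning for a descriptive estimate.** On the scale of the score, the standard error grows by 1/√e: 1/0.798 = 1.25 at 10/10 and 1/0.700 = 1.43 at 4/16.

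**Sensitivity to score shape.** Losses over splits from 50/50 to 20/80 were 25–52% for a uniform score, 36–45% for a moderately skewed (gamma) score, 35–52% for an exponential score and 19–56% for a clearly bimodal score.

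**Illustrative power.** This only gives a sense of scale, because the plan proposes no test. Simulation with n = 20, bivariate normal data and two-sided 0.05:

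| True r (assumed) | Spearman | 10/10 split | 4/16 split |
|---|---|---|---|
| 0.3 | 23% | 17% | 14% |
| 0.5 | 57% | 42% | 31% |
| 0.6 | 77% | 60% | 45% |

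**Are the bands in Section 2.1 usable?** The GAD-7 bands are 0–4, 5–9, and then "moderate (10-14) and serious (14-20". A score of 14 is in two bands, and 21 is in none although the stated range reaches it. The PHQ-9 bands are 5–9, 10–14 and 15–19, and then "a score > 20 indicates major depression", which leaves 20 in none. The edges at 5 and 10 on both scales, and at 15 on the PHQ-9, are clean. With any of these cuts, the misplaced scores fall plainly in the high group.

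**The case against.** The strongest defence is that item 4 is exploratory and descriptive. It has no test, significance level or power claim, so comparing the power of tests criticises something the plan does not propose. This stands for the power figures. It does not remove the loss, because a descriptive difference from a split is also less precise.

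The size of the loss is assumed rather than documented. This stands too. A reader might take a loss of a third to a half as established, but the documents give neither the cut nor the score distribution. The formula also assumes a continuous outcome. Response and diarrhea grade, which item 4 would cover, are categorical, so the figures do not carry over to them exactly.

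A reader might also infer from the faulty bands that the protocol cannot supply a cut. The documents do not support that: clean lower edges exist, and Section 2.1 gives a yes/no depression rule that needs no bands. The gap is that none of these is named. The band errors are in background text, and the PHQ-9 sign may have been altered when the PDF was read.

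Section 8.1 (Other endpoints) does mention correlation of taxa with phenotypic variables. It does not name either questionnaire, so it does not fill the gap.

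Finally, the gain is modest. At r = 0.3, Spearman reaches only about 23% power. This limits the benefit but is no reason to prefer the split.

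**Conclusion.** The point holds as a cheap improvement to an exploratory analysis. Item 4 relies on a split with no stated cut or time point, and plans no analysis of totals that are already collected. With a near-normal score and a linear association, the split leaves the equivalent of about 12.7 of 20 patients at 10/10 and 9.8 at 4/16. More uneven splits leave fewer, and other score shapes move the loss within about 19–56% over splits from 50/50 to 20/80. The actual loss cannot be fixed from the documents.

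No stated power figure is wrong, and the primary comparison of *Bifidobacterium* is not touched. The priority is low.

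**What to change.** Reword Section 8.1, item 4 along these lines:

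- Analyse the PHQ-9 and GAD-7 totals as recorded, and name the assessment used (baseline or week 13) for each comparison.
- Report Spearman correlations with 95% confidence intervals against microbial diversity, *Bifidobacterium* abundance, immune markers and worst diarrhea grade.
- Summarise the scores by diarrhea (yes/no) and by response. Section 5.2 records four response categories, so state in advance whether and how they are grouped.
- Label all of this exploratory, without multiplicity control.
- Keep any low/high table as a descriptive display, at a cut fixed in advance.

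As a secondary correction, repair the band limits in Section 2.1 so that each score falls in exactly one band.

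No new visits, samples or patients are needed. The cost is a small protocol text change, which goes through the IRB, and correlations are slightly less familiar to clinicians than two groups. The change does not make 20 patients enough to detect modest associations.

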#### Other endpoints:

# Clustering short read sequences, identify operational taxomomic units (OTUs) and summarize microbiome profiles.

QIIME will be used to cluster V5-16S rRNA Solexa reads for each sample, at the level of 97% nucleotide sequence identity. A closed-reference OUT picking protocol with USEARCH against Greengenes database will be used. Taxonomy will be assigned using RDP classifier 2.4. The relative abundance of OTUs will be calculated at phylum-, class-, order-genus- and species-level taxa. Weighted and unweighted UniFrac distances between samples will be calculated with a *de novo* tree constructed from representative sequences defining each OTU. A table of OTU counts per will be generated and used in combination with the tree to calculate beta diversity. The association between the subclusters and phenotypic variables will be studied. Principle coordinate analysis (PCoA) will be used to examine possible correlation between phylum/genus and other phenotypic variables.

# Asssess the feasibility of stool collection and bacteriomic profiling.

We will assess the feasibility of bacteriomic profiling. Specifically, we will make note of those stool specimens for could not be performed. Reasons for an inability to perform this analysis will be noted (for instance, insufficient DNA collection) and the number of specimens that could not be analyzed will be expressed as a proportion of the overall specimens collected. These data will be integral for the future directions of this project, where stool collection will be performed for the same purposes in larger cohorts.

#### 8.2 Sample Size and Projected Accrual Rate and Study Duration

Twenty participants will be metastatic renal cell carcinoma will enroll to the study. Enrollment is expected to be completed in 3 years, and the study is expected to be completed in 3.5 years.

#### 9.0 HUMAN SUBJECT ISSUES

#### 9.1 Recruitment of Subjects

Potential participants will be approached by their physicians or a member of the clinical staff and invited to participate within the outpatient clinic environment.

#### 9.2 Advertisements

No publicly displayed advertisements will be used to recruit potential study participants.

#### 9.3 Informed Consent

All participants will undergo standard written informed consent procedures as dictated by the City of Hope Human Research Protections Office prior to performing any screening procedures that are not part of standard-of-care. Informed consent will be obtained by the principal investigator, collaborating

IRB Protocol No. 16088 Version Date: 06/12/2020

investigators, or other IRB designated personnel who will meet the training requirements established by the IRB. With the support of research personnel, he/she will explain the nature, duration, purpose of the study, potential risks, alternatives and potential benefits, and all other information contained in the informed consent document. In addition, they will review the experimental subject's bill of rights and the HIPAA research authorization form. Prospective research participants will be informed that they may withdraw from the study at any time and for any reason without prejudice. Prospective research participants will be afforded sufficient time to consider whether or not to participate in the research.

#### 9.4 Participant Withdrawal from Research

At any time after signing the informed consent document, participants may elect to withdraw from future study procedures (stool sample) but permit clinical data collection to continue, or may elect to withdraw completely from the study whereby no additional samples or data will be collected. In this later instance, data and samples already collected will continue to be used as this information will have been deidentified with the exception of the RPN. Participant withdrawal, including the nature of withdrawal, will be documented by the investigator as per standard COH practice.

#### 9.5 Study location and Performance Sites

Participant involvement and data collection and blood sample analysis will be performed at City of Hope. Stool sample processing and analysis will be performed in [name] laboratory at TGen North in Flagstaff, AZ.

#### 9.6 Potential Risks and Benefits to Participation

#### 9.6.1 Potential risks to participation

The risks and discomforts of this study are minimal. The risks of drawing blood include temporary discomfort from the needle stick, minor bleeding, bruising, anemia, dizziness, and very rarely, an infection where the needle was inserted. All blood specimens requested for this study will be collected at the time of routine procedures, as such there will not be any additional needle stick, and the risk to the participant will be minimized.

The risks of establishing a data specimen repository and medical record data collection are minimal and include a possible breach of confidentiality. The risk of breach in confidentiality will be mitigated by following procedures detailed in Section 9.10.

The risks of a dietary intervention with a yogurt product are minimal and include allergic reactions (if not previously known) and minor GI-related complaints.

Furthermore, the anxiety and depression assessment have a potential risk of a temporary emotional discomfort.

#### 9.6.2 Potential benefits to participation

There is no direct significant benefit to the research participant. However, the participant may benefit from the knowledge that his/her participation may help others.

# 9.6.3 Potential benefits to others

Information from this study is expected to contribute to the identification of biomarkers that may help inform treatment decisions by clinicians treating patients for cancer for which one treatment option involves a VEGF-TKI agent.

# 9.7 Alternatives to Participation

The patient can choose not to participate, and this will not impact their medical care in any way.

IRB Protocol No. 16088 Version Date: 06/12/2020

#### 9.8 Financial Obligations and Compensation

In the event of physical injury to a research participant, resulting from research procedures, appropriate medical treatment will be available at the City of Hope to the injured research participant, however, financial compensation will not be available.

The research participant will not be paid for taking part in this study. If randomized to the probiotic-supplemented group, reimbursement will be provided for this intervention if requested by the patient.

# 9.9 Registration into MIDAS

Research participants will be registered into MIDAS for this trial.

#### 9.10 Confidentiality

This research will be conducted in compliance with federal and state of California requirements relating to protected health information (PHI).

All samples will be coded prior to submission to the research laboratories. The coded identifier will be the COH research patient number (RPN), provided by the MIDAS system, which is devoid of direct participant identifiers. The key to the code is maintained in MIDAS which is a secure environment.

All study related forms including consent documents and patient pill diaries will be stored in locked and secure locations.

Medical records of participants will be securely maintained in the strictest confidence, according to current legal requirements. All information will be treated confidentially. No identifiers will be used in any subsequent publication of these results.

#### 10.0 DATA AND SAFETY MONITORING, UNANTICIPATED PROBLEMS AND ADVERSE EVENT REPORTING

#### 10.1 Definition of Risk Level

This is a Risk Level 2 study, as defined in the City of Hope Institutional Data and Safety Monitoring Plan [policy effective date: 07/09/14], because it involves blood sample collection, establishment of a data specimen repository, medical record data collection, and a dietary intervention with yogurt where the risk of harm is low.

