#### 5.0 CLINICAL DATA COLLECTION

#### 5.1 Participant Daily Diary

Participants will be oriented to complete the daily study log, found in Appendix B. The log will be collected and reviewed during visits to the clinic at the end of each 3-week treatment regimen (weeks 3, 6, 9 and 13 of treatment). The following information from the diary will be entered into the study specific database for analysis:

- Diarrhea, categorized per CTCAE 4.0 diarrhea grading. Please note that the patient will be instructed to consider diarrhea to be an increase in stool frequency of < 4 over baseline. This definition is consistent with the CTCAE 4.0 terminology for grade 1 diarrhea.
- Stool specimen collection dates
- Yogurt intake, or intake of yogurt-containing foods

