#### 5.2 Data Collected from the Medical Record

The following data will be obtained from the medical record and recorded in the study specific database:

- Age at registration, gender
- Prior anti-cancer therapy
- Concurrent medications from the time of informed consent through end of participation
- VEGF-TKI dose and administration
- Smoking status
- Response status (as noted by treating investigator: PD, SD, CR, PR)

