#### 10.3 Unanticipated Problems (UP) Involving Risks to Subjects or Others

An unanticipated problem is any incident, experience or outcome that meets all three of the following criteria:

- Unexpected (in terms of nature, severity, or frequency) given the following: a) the research
  procedures that are described in the protocol-related documents such as the IRB approved
  research protocol, informed consent document or Investigator Brochure (IB); and b) the
  characteristics of the subject population being studied; AND
- 2. Related or possibly related to participation in the research (possibly related means there is a reasonable possibility that the incident, experience, or outcomes may have been caused by the procedures involved in the research); AND

IRB Protocol No. 16088 Version Date: 06/12/2020

3. Suggests that the research places participants or others at greater risk of harm (including physical, psychological, economic, or social harm) than previously known or recognized.

Any UP that occurs during the study conduct will be reported to the DSMC and IRB in accordance with the City of Hope's Institutional policy [policy effective date: 05/14/14] using the electronic submission system, iRIS.

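### Apart from diarrhea and incontinence, the yogurt harms named in Section 9.6.1 have no data field, no summary by arm and, when they occur as anticipated, no reporting route in the protocol

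*Combined protocol and SAP*

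**What the plan says.** Section 9.6.1 sets out what the yogurt might do: "The risks of a dietary intervention with a yogurt product are minimal and include allergic reactions (if not previously known) and minor GI-related complaints". Section 10 is headed "DATA AND SAFETY MONITORING, UNANTICIPATED PROBLEMS AND ADVERSE EVENT REPORTING". Its subsections deal with risk level, monitoring responsibility, unanticipated problems, deviations and single-subject exceptions.

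The one route for events is Section 10.3: "Any UP that occurs during the study conduct will be reported to the DSMC and IRB". Three criteria must all be met. The first is "Unexpected (in terms of nature, severity, or frequency) given the following", with the protocol itself among the references. The second is a possible relation to the research. The third is "Suggests that the research places participants or others at greater risk of harm" than was already known.

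Two lists define the data:
- Section 5.1 opens "The following information from the diary will be entered into the study specific database for analysis" and names diarrhea grade, stool specimen dates and yogurt intake.
- Section 5.2 opens "The following data will be obtained from the medical record and recorded in the study specific database" and names age and gender, prior therapy, concurrent medications, VEGF-TKI dose, smoking and response.

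The Appendix B log, kept by both arms, asks about food, yogurt or probiotics, stool frequency (with incontinence in the top category), samples and medications. The Appendix D log, kept by the Activia arm, asks for serving size and time.

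**The concern.** The protocol names two kinds of harm from its randomised intervention, and its data collection covers only part of one of them. A site that follows the plan exactly would enter no record of a rash after yogurt, or of bloating, nausea or cramps, as an event. Such events may not be recoverable later.

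Three consequences follow:
- The report could describe possible benefit by arm (*Bifidobacterium*, diarrhea) but could not describe these harms by arm.
- Secondary objective 4 in Section 8.1 analyses gastrointestinal toxicity, yet diarrhea is the only such toxicity the plan collects. That analysis also splits patients by depression and anxiety, not by arm.
- A patient who stops yogurt because of a reaction cannot be told apart, in the listed data, from one who simply lost interest.

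All participants are also starting a VEGF-TKI, so GI symptoms in the Activia arm are hard to interpret without the same record in controls. The randomised control arm offers that comparison, and the plan does not use it.

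**Working it through.** **1. The plan's own figure.** The only planned comparison of a GI event by arm is diarrhea in Section 8.1: Fisher's exact test, one-sided 0.05, 10 per arm, 0.20 against 0.80, stated power 80%. Enumerating all pairs of Binomial(10, 0.20) and Binomial(10, 0.80) outcomes gives 80.5%, so the figure reproduces. It concerns a reduction in diarrhea, treated as an efficacy outcome, and says nothing about other harms.

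**2. Each named harm against the plan.**

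| Item | Allergic reaction | GI complaint other than diarrhea/incontinence | Diarrhea |
|---|---|---|---|
| Activity table (4.1) | no row | no row | stool sample at onset |
| Diary items entered (5.1) | no | no | yes, CTCAE grade |
| Medical record items (5.2) | no | no | no |
| Appendix B log | no | incontinence only | yes, daily |
| Appendix D log | no | no | no |
| Comparison by arm (8.1) | no | no | yes, all grades and grade 3/4 |

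**3. The reporting route.** Section 9.6.1 says the risks "include allergic reactions (if not previously known) and minor GI-related complaints". An event of that kind, at the severity and frequency anticipated, is not unexpected given the protocol and does not suggest a greater risk than already known. It fails criteria 1 and 3 of Section 10.3. The principal investigator's reporting duty in Section 10.2 is limited to what the later subsections indicate, and none of them covers adverse events.

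**4. What collection would offer.** The documents give no event rate, so the rates here are assumptions. With n = 10 in the Activia arm, the probability of at least one event is 1 − (1 − p)^10:
- p = 0.05: 1 − 0.95^10 = 0.40
- p = 0.10: 1 − 0.90^10 = 0.65
- p = 0.20: 1 − 0.80^10 = 0.89
- p = 0.30: 1 − 0.70^10 = 0.97

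If 0 of 10 patients had an event, the exact upper limits would be:
- one-sided 95%: 1 − 0.05^(1/10) = 0.259
- two-sided 95%: 1 − 0.025^(1/10) = 0.308

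**5. What collection would not offer.** Under assumed rates of 10% in controls and 30% with yogurt, a one-sided Fisher test at 0.05 with 10 per arm has about 14% power. A formal test by arm would be of little use; counts with intervals are the realistic product.

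**The case against.** The strongest reply is that a reader might infer too much from this gap. Several points in it stand:

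- **Harms recorded nowhere.** The documents do not support this. Diarrhea is itself a GI complaint. It is logged daily in both arms, graded and compared by arm.
- **All yogurt reactions escape reporting.** This does not follow either. The definition in Section 10.3 includes unexpected severity or frequency, so a severe allergic reaction, or an unexpected excess of complaints, could qualify. The frequency limb is weakened, however, because the plan gives no expected frequency and collects no count against which an excess could be seen.
- **The monitoring committee would never see such events.** The documents cannot settle this. Section 10 relies on institutional policies whose text is not available, and they may impose adverse event duties.
- **Indirect traces exist.** Concurrent medications may show a treated reaction. Appendix D shows when yogurt intake stops. Section 9.4 documents the nature of a withdrawal from the research. None of these records the event, its grade or the reason for stopping yogurt.
- **Scale and risk.** This is a 20-patient trial with a microbiological primary endpoint. Section 10.1 rates the risk of harm as low, and patients with known intolerance to Activia constituents are excluded. That limits the urgency.
- **Bias.** No placebo is described, so self-reported complaints may be influenced by knowledge of the arm. Any summary should be read with that in mind.

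**Conclusion.** The point holds in a limited form. Allergic reactions, and GI complaints other than diarrhea and incontinence, have no field and no summary by arm. At anticipated severity and frequency they have no reporting route in this protocol. The adverse event text promised by the Section 10 title is absent.

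It would go too far to conclude that the trial cannot monitor or compare the safety of its intervention. Diarrhea is covered, unexpected events have a route, and institutional rules are unseen. The weakness of a formal comparison comes mainly from 10 patients per arm, not from the missing fields.

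The practical loss is descriptive. Zero events in 10 would support an upper bound of 26% (one-sided) or 31% (two-sided), and the plan as written supports none for these events. The event probabilities of 40% to 97% rest on assumed rates of 5% to 30%. At a rarer assumed rate of 1%, the chance of seeing any event in 10 patients is about 10% (1 − 0.99^10). This is a cheap improvement worth making, not a flaw that threatens the primary analysis.

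**What to change.** - **Appendix B and Section 5.1:** add one symptom field to the log that both arms complete, and add that field to the list of diary items entered in the database.
- **Section 5.2, both arms:** add allergic or hypersensitivity reaction, and new GI complaint other than stool frequency, each with date and CTCAE grade.
- **Activia arm only:** record the investigator's judgement of relation to the yogurt, and the reason if intake is stopped. Relation to yogurt cannot sensibly be asked of controls, who are told to eat none.
- **Section 10:** state that these events are tabulated by arm for the DSMC, and name any institutional adverse event policy that applies.
- **Section 8.1:** state that counts by arm are reported descriptively with exact 95% intervals and no formal test, and say which items make up gastrointestinal toxicity.

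The cost is slightly more data entry in 20 patients. No new visit or procedure is needed, and no treatment rule changes.
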